### **Screening Assessments**

1. Demographic data and clinical characteristics will be recorded for each subject (baseline visit).
2. Formal screening psychiatric interview for each subject including the Mini International Neuropsychiatric Inventory (10) (baseline visit).
3. Symptom severity at baseline and follow-up visits will be examined using reliable and valid scales:
  - a. *Massachusetts General Hospital Hairpulling Scale* (MGH-HPS) (11) (each visit)

- b. *Trichotillomania Scale for Children, Child Version (TSC-C)* (12) (each visit) (only for children under the age of 18 who are participating in the study)
- c. *Trichotillomania Scale for Children, Parent Version (TSC-P)* (12) (each visit) (only for parents of children under the age of 18 who are participating in the study)
- d. *NIMH Trichotillomania Symptom Severity Scale (TSS)* (13) (each visit)
- e. *Clinical Global Impression severity and improvement scales* (14) (each visit)
- f. *Sheehan Disability Scale* (15) (baseline and final visit)
- g. *Hamilton Anxiety Rating Scale (HAM-A)* (16) (each visit)
- h. *Hamilton Depression Rating Scale (HAM-D)* (17) (each visit)
- i. *Lie Acceptability Scale (Baseline)*
- j. *The Narcissistic Personality Inventory 16 (Baseline)*
- k. *The Social Desirability Scale (Baseline)*

*Massachusetts General Hospital Hair Pulling Scale (MGH-HPS)* (11). The MGH-HPS is a 7-item, self-report scale that rates urges to pull hair, actual amount of pulling, perceived control over behavior, and distress associated with hair pulling over the past seven days. Analysis of the MGH-HPS has demonstrated two separate factors with acceptable reliability for both: “severity” and “resistance and control.”

*Trichotillomania Scale for Children (TSC-C & TSC-P) (Parent and Child Versions)* (12). The TSC is a validated measure of trichotillomania symptom severity in children. These scales assess parent and child reports of frequency of pulling behavior as well as other facets of severity and impairment. (Tolin et al., 2008)

*NIMH Trichotillomania Severity Scale (NIMH-TSS)* (13). The NIMH scale is a 5-item, clinician-administered scale that rates hair pulling symptoms during the past week. The items assess pulling frequency (both on the previous day and during the past week), urge intensity, urge resistance, subjective distress, and interference with daily activities. Four items are rated from 0 (none) to 5 (most severe) and the final item is rated from 0 to 4. A total score is calculated by summing all the item scores. The NIMH-TSS has demonstrated sensitivity to changes in symptom severity.

*Clinical Global Impression- Severity and Improvement (CGI)* (14). The CGI consists of a reliable and valid 7-item Likert scale used to assess severity and improvement in clinical symptoms. The CGI severity scale was used at each visit and ranges from 1 = “not ill at all” to 7 = “among the most extremely ill.” The CGI Improvement scale was used at each follow-up visit and ranges from 1 = “very much improved” to 7 = “very much worse.”

*Sheehan Disability Scale (SDS)* (15). The SDS is a three-item, reliable and valid self-report scale that assesses functioning in three areas of life: work, social or leisure activities, and home and family life. Scores on the SDS range from 0 to 30.

*Hamilton Anxiety Rating Scale (HAM-A)* (16). The HAM-A is a reliable and valid, clinician-administered, 14-item scale that provides an overall measure of global anxiety.

*Hamilton Depression Rating Scale (HAM-D) (17)*. The HAM-D is a valid and reliable, 17-item, clinician-administered rating scale assessing severity of depressive symptoms.

*Cambridge-Chicago Trait Scale (Cambridge CHI-T Scale) (18)*. The CHI-T scale is a 16-item self-report scale that measures compulsivity.

*Lie Acceptability Scale (Goosie, 2014)*: An 11-item self-report questionnaire which assesses an individual's perception of the acceptability of lying across several dimensions.

*The Narcissistic Personality Inventory 16 (Raskin & Terry, 1988)*: The NPI-16 is a short measure of subclinical narcissism that has shown meaningful face, internal, discriminant, and predictive validity. It can serve as an alternative measure of narcissism when situations do not allow the use of longer inventories.

*The Social Desirability Scale (Crowne & Marlowe, 1960)*: A 33-item self-report questionnaire which assesses the degree to which individuals report the outcome that is most socially desirable using true/false questions.

*Cognitive Assessments*: In addition, subjects will undergo cognitive assessments at baseline and study endpoint. Assessments of cognitive control will be comprised of several valid paradigms (Table 1). These tasks are designed to probe dissociable neural circuitry and cognitive processes likely to be implicated in the pathophysiology of body-focused repetitive behaviors. Task order will be chosen arbitrarily and will be applied consistently across subjects, to minimize possible confounding factors of differences in task order across participants.

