Aim 2: Because lack of cognitive control may underlie a range of body-focused repetitive behaviors, and improvement in related systems may be secondary to greater control, we will examine levels of cognitive control using cognitive tasks pre- and post-treatment. This study will examine cognitive deficits across a range of prefrontal-dependent domains which have been associated with trichotillomania – response inhibition, working memory, cognitive flexibility and planning ability - as possible predictors of treatment and as possible biomarkers for underlying pathophysiology of hair pulling behavior. We hypothesize that improvement in response inhibition will be greater in participants who receive milk thistle compared with placebo.

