### **Methodology**

The proposed study will consist of a 13 week double-blind cross-over study trial of milk thistle in 25 people (ages 10-65). The study will be divided into an initial 6 week phase, a 1 week wash-out phase, and a second 6 week phase, with one of the 6 week phases consisting of active treatment with milk thistle, and one of the 6 week phases consisting of inactive placebo treatment. Participants will be randomized to receive either milk thistle or placebo during the first 6 week phase on a 1:1 basis. This blinding will be maintained by the IDS pharmacy at the University of Chicago.

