### **Study Design**

The study is a 13-week, double-blind, placebo-controlled, pilot study of the safety and efficacy of milk thistle for children and adults with trichotillomania. All eligible study subjects will go through a 6-week treatment phase during which they will begin milk thistle at 300mg twice a day. Subjects will be given a matching placebo during the 6-week placebo phase. Subjects will be seen for scheduled study visits every two weeks during the 6-week blinded phases, with an additional visit one week after the end of the first 6 week phase, corresponding with the end of the 1 week wash-out period. Subjects will be randomized to either receive either the active or placebo condition during the first 6-week phase, and the remaining condition during the second 6-week phase. All efficacy and safety assessments will be performed at each visit. Subjects who are not compliant with their use of study medication (i.e. failing to take medication for three or more consecutive days) will be discontinued from the study. Patients who experience a clinically significant adverse event will also be discontinued from the study.

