### Data Analysis

Demographic and baseline visit characteristics for milk thistle and placebo groups will be compared using chi-square and analysis of variance to determine if group differences existed at randomization. Given the crossover design, both the placebo and the active milk thistle groups will contain an N of 25. Primary and secondary measures will be examined using repeated-measures ANOVA modeling analyses (PROC MIXED, SAS/STAT Software for Windows, Version 8.2, SAS Institute Inc., Cary, NC, USA). The baseline value of the measure being analyzed will be used as a covariate. A time trend (linear) will be included in all models. The difference in the overall level of posttreatment values, the main effect for treatment, will be the test of primary interest. Analyses will be performed on all available data as well as for the completers. All available post-randomization data will be first analyzed and a secondary, supportive analysis of completers will be performed. All comparison tests will be two-tailed and an alpha level of .05 will be used to determine statistical significance given the exploratory nature of the study.

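### The cognitive tasks are given only at baseline and study endpoint, so Aim 2's response-inhibition hypothesis has no within-patient drug-placebo comparison

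*Combined protocol and SAP*

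**What the plan says.** **Hypothesis.** Specific Aims, Aim 2: "We hypothesize that improvement in response inhibition will be greater in participants who receive milk thistle compared with placebo". On timing, the same aim says "we will examine levels of cognitive control using cognitive tasks pre- and post-treatment".

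**Task schedule.** Screening Assessments, Cognitive Assessments: "subjects will undergo cognitive assessments at baseline and study endpoint". Table 1 assigns response inhibition to the stop-signal task, which belongs to that battery.

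**Design.** Methodology: "The study will be divided into an initial 6 week phase, a 1 week wash-out phase, and a second 6 week phase". Each patient takes milk thistle in one phase and placebo in the other, with 1:1 randomisation to order. Study Design: "Subjects will be seen for scheduled study visits every two weeks during the 6-week blinded phases", plus a visit at the end of wash-out. A week-6 visit therefore exists.

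**Analysis.** Data Analysis relies on the crossover to state that "both the placebo and the active milk thistle groups will contain an N of 25", and describes a model for primary and secondary measures. Efficacy Assessments names no cognitive task among them.

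**Sheehan Disability Scale.** It is listed as a secondary efficacy measure. Study Design says "All efficacy and safety assessments will be performed at each visit", but item f of Screening Assessments gives the scale at "baseline and final visit".

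**The concern.** A crossover gains its precision by measuring each patient under both conditions. Two task sessions, one before any treatment and one after both phases, cannot do that. The change between them mixes milk thistle, placebo, practice on the tasks and the passage of time.

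The only hypothesis stated under Aim 2 would then rest on a small between-sequence comparison that the plan does not describe. A null result would say little, and an improvement from baseline to endpoint could be misread as a drug effect. If item f governs the Sheehan scale, the same limit applies to a listed secondary outcome.

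**Working it through.** **Count of scores.** This step needs no assumption.

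| Time | Milk thistle first | Placebo first | Tasks given? |
|---|---|---|---|
| Week 0 | untreated | untreated | yes |
| Week 6, end of phase 1 | on milk thistle | on placebo | no |
| Week 7, end of wash-out | off treatment | off treatment | no |
| Week 13, end of phase 2 | on placebo | on milk thistle | yes |

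Each completer has one on-treatment score, under the second condition only. Completers with a score under both conditions: 0 of 25. For the tasks, 25 per condition becomes about 12 and 13. A patient who left early might be tested after one condition only, which adds no within-patient contrast either.

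**Precision lost.** The plan gives no power, SD or effect size for its 25 patients, so there is no figure to reproduce. From the documents: N = 25, 1:1 allocation, two-sided alpha 0.05. Assumed: SD = 1, correlation rho of 0.4 to 0.7 between any two scores of a patient, true effect 0.5 SD, no dropout unless stated.

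- Between sequences at week 13, adjusted for baseline: variance = (1 − rho²)(1/n1 + 1/n2), with N − 3 = 22 df.
- Crossover contrast, if week 6 were also measured: variance = [(1 − rho)/2](1/n1 + 1/n2), with N − 2 = 23 df.
- Ratio: (1 − rho²) ÷ [(1 − rho)/2] = 2(1 + rho).

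At rho 0.5, 1/12 + 1/13 = 0.1603. The variances are 0.75 × 0.1603 = 0.1202 (SE 0.347) and 0.25 × 0.1603 = 0.0401 (SE 0.200). Power comes from the noncentral t distribution. Each pair below is week 13 between sequences v crossover.

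| Patients | rho | Variance ratio | SE | Effect detectable at 80% power (SD) | Power for 0.5 SD |
|---|---|---|---|---|---|
| 12 v 13 | 0.4 | 2.8 | 0.367 v 0.219 | 1.08 v 0.64 | 26% v 59% |
| 12 v 13 | 0.5 | 3.0 | 0.347 v 0.200 | 1.02 v 0.59 | 28% v 67% |
| 12 v 13 | 0.7 | 3.4 | 0.286 v 0.155 | 0.84 v 0.45 | 39% v 87% |
| 10 v 10 (20% dropout) | 0.5 | 3.0 | 0.387 v 0.224 | 1.15 v 0.66 | 23% v 56% |

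**Carryover.** Let a share c of the effect d persist to week 13 in patients who took milk thistle first; c is a further assumption.

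- Week 13 between sequences: d − cd = (1 − c)d.
- Crossover: half of [(d − cd) − (0 − d)] = (1 − c/2)d.

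For d = 0.5 SD, the week-13 comparison estimates 0.375 SD at c = 0.25 and 0.25 SD at c = 0.5; the crossover estimates 0.44 and 0.375 SD. A week-6 comparison between groups has no carryover and the same standard error as week 13 (0.35 SD at rho 0.5). Simulating 6,000 trials at rho 0.5 and c = 0.5 gave mean estimates of 0.253 (week 13), 0.375 (crossover) and 0.498 (week 6).

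**The case against.** - **Aim 2's timing could be read per phase, and the study endpoint is not defined.** That reading is possible. But the assessment section is the more specific text and the only explicit schedule. If testing in each phase is intended, the protocol has to say so. The rule that efficacy assessments are done at every visit does not clearly reach the tasks, which are not in the efficacy list and have their own timing.
- **The list of secondary measures may not be exhaustive.** If the tasks count as secondary, the planned model with one post-treatment score reduces to roughly the between-sequence comparison above. This softens the point about analysis: the tasks are not named in it. If they are not secondary, the count of 25 per condition was never claimed for them. On either reading, no completer has both scores.
- **The carryover shares have no support in the documents.** This stands. Week 13 is seven weeks after phase 1 dosing ends, so c = 0.5 is a strong assumption; the figures are conditional illustrations. Carryover also biases the crossover contrast, by half as much.
- **The repair does not make the comparison well powered.** This stands too: at rho 0.5 the crossover has 67% power for 0.5 SD, and the week-6 check alone about 28%.
- **This is an exploratory pilot.** That supports a wording-only repair, but not leaving a directional hypothesis without a described comparison.

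**Conclusion.** The concern holds. On the only explicit schedule, the hypothesis under Aim 2 has no within-patient comparison; this follows from counting visits and rests on no assumption. The size of the loss does: with rho between 0.4 and 0.7, the remaining comparison has 2.8 to 3.4 times the variance of a crossover contrast, and at rho 0.5 the power for an assumed 0.5 SD effect is 28% instead of 67%.

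The primary outcome (NIMH-TSS, rated at each visit) and the use of baseline cognition as a predictor of response are untouched. The Sheehan conflict is a separate and smaller matter. This should be fixed, but it does not threaten the main result.

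**What to change.** **Cognitive tasks.** Define the study endpoint, reconcile Aim 2 with the assessment section, and choose one:

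- (a) Repeat the battery, or at least the stop-signal task, at the existing week-6 visit. Analyse it with the crossover model including phase, and report the week-6 comparison between groups as a check free of carryover. Phase removes only average practice, and carryover bias is halved, not removed. Cost: one more session per patient at a visit already planned, including participants as young as 10, with added practice. The documents give no session length; the stop-signal task alone would limit the burden.
- (b) Keep two sessions and restate the hypothesis as an exploratory between-sequence comparison at week 13, on about 12 v 13 patients, with baseline as covariate. Cost: wording only.

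In either case, name the analysis of the tasks and state that a plain change from baseline to endpoint will not be read as a drug effect.

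**Sheehan scale.** Reconcile Study Design with item f so that the scale is taken at least at weeks 0, 6 and 13. Cost: three self-report items at an existing visit.

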**Table 1. Neurocognitive Tasks**

Task	Target Cognitive Process
MOT	Training Task.
Intra-dimensional/Extra-dimensional Set Shift Task (ID/ED task)	Intra- and extra-dimensional thinking ability. Assesses cognitive flexibility.
Stop-Signal Task of Inhibitory Control	Motor impulsivity and response inhibition.
Tower of London Task	Problem solving and logic task.
Cambridge Gamble Task	Decision making and risk adjustment.
RVP	Visual processing abilities.
SWM	Spatial working memory abilities.

### **Efficacy Assessments**

**The primary outcome measure will be the NIMH Trichotillomania Severity Scale (NIMH-TSS)**. The NIMH-TSS is a reliable and valid scale that is frequently used in research to assess symptom severity.

Secondary efficacy measures include

- *The Clinical Global Impression-Improvement and Severity scales (CGI)*
- *Massachusetts General Hospital Hair Pulling Scale (MGH-HPS)*

- *Trichotillomania Scale for Children (TSC-C & TSC-P) (Parent and Child Versions)*
- *Sheehan Disability Scale (SDS)*
- *Hamilton Anxiety Rating Scale (HAM-A)*
- *Hamilton Depression Rating Scale (HAM-D).*
- *Cambridge-Chicago Trait Scale (Cambridge CHI-T Scale)*

### **Safety Assessments**

Safety assessments (sitting blood pressure, heart rate, adverse effects, and concomitant medications) will be documented at each visit.

Suicidality will be assessed using the Columbia Suicide Severity Rating Scale. This scale will be performed at every visit. Subjects who endorse suicidal thoughts at any time during the study will be removed from the study and appropriate clinical intervention (e.g. hospitalization) will be arranged.

The investigator will record use of concomitant medications in terms of daily dosage, start and stop dates, and reason for use. Adverse events will be recorded at each study visit and as they become known to the study staff. Medication compliance will be ascertained through weekly pill count of investigational medication.

### **Risks and Benefits**

#### *Risks*

Potential risks during the study include side effects from the active milk thistle. The most common side effects include:

- Upset stomach
- Diarrhea
- Headaches
- Bloating

In rare cases, other side effects may occur. In the event of one of these changes, participants and guardians will be instructed to contact the study doctor immediately:

- A skin rash
- Respiratory distress.

It is also possible that the questions regarding symptoms related to trichotillomania, depression, or mental health may be distressing, especially for children. Special precautions will be taken to allow the child to adjust to the study environment and provide opportunities for the child to check in with study staff about any current discomfort. There may be other risks that could arise which are not reasonably foreseeable. If new information becomes available, study staff will make this information available to participants and legal guardians immediately.

#### *Benefits*

Potential benefits include a possible direct medical benefit. Specifically, the study drug may help curb the severity of symptoms related to trichotillomania, but there can be no guarantee that this will be the case.

This research provides substantial benefit for current treatments for trichotillomania, particularly in children. As there is currently little to no research in this area, the current study could offer significant advancement in possible treatments for this disorder.

### Data Analysis

Demographic and baseline visit characteristics for milk thistle and placebo groups will be compared using chi-square and analysis of variance to determine if group differences existed at randomization. Given the crossover design, both the placebo and the active milk thistle groups will contain an N of 25. Primary and secondary measures will be examined using repeated-measures ANOVA modeling analyses (PROC MIXED, SAS/STAT Software for Windows, Version 8.2, SAS Institute Inc., Cary, NC, USA). The baseline value of the measure being analyzed will be used as a covariate. A time trend (linear) will be included in all models. The difference in the overall level of posttreatment values, the main effect for treatment, will be the test of primary interest. Analyses will be performed on all available data as well as for the completers. All available post-randomization data will be first analyzed and a secondary, supportive analysis of completers will be performed. All comparison tests will be two-tailed and an alpha level of .05 will be used to determine statistical significance given the exploratory nature of the study.

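### The primary crossover model names no phase term, no covariance for visits in the same phase and no small-sample method, so an ordinary fit can exceed the stated .05

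*Combined protocol and SAP*

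**What the plan says.** The Data Analysis section is the only analysis text. It states: "Primary and secondary measures will be examined using repeated-measures ANOVA modeling analyses", to be run in PROC MIXED. It adds two terms: "The baseline value of the measure being analyzed will be used as a covariate" and "A time trend (linear) will be included in all models". The primary test is then defined: "The difference in the overall level of posttreatment values, the main effect for treatment, will be the test of primary interest". Testing is two-sided at .05, a level the section justifies by the exploratory purpose of the study.

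The design comes from Methodology and Study Design. There are 25 patients, randomised 1:1 to the order of milk thistle and placebo, with two six-week phases and a one-week washout between them. On visits, Study Design says: "Subjects will be seen for scheduled study visits every two weeks during the 6-week blinded phases". That gives three on-treatment visits per phase, at study weeks 2, 4, 6, 9, 11 and 13. One more visit falls at the end of washout.

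No section names a phase (period) effect, the random effects or covariance structure, or a method for standard errors and degrees of freedom.

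**The concern.** In this design a patient's treatment is constant within a phase and changes only between phases. The precision of the treatment effect therefore depends on how much a patient's level moves from one phase to the other for reasons other than treatment. Three visits in a phase help to average out visit-to-visit noise. They do not average out a shift that affects all three.

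A repeated-measures model with a patient intercept and nothing else assumes that no such shift exists. If it does exist, the standard error is too small and the test rejects too often. At the other extreme, an unstructured covariance over six visits allows the within-phase correlation but estimates 6 x 7 / 2 = 21 parameters from 25 patients, so its uncorrected standard error is also too small. The plan does not choose among these fits and names no correction. At stake is whether the primary p-value can be read against the .05 that the plan sets.

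**Working it through.** The plan gives no power, effect size or variance, so it has no figure to reproduce other than the declared .05.

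**Inputs from the documents.** 25 patients, two phases, three on-treatment visits per phase, 1:1 allocation (taken as 12 and 13), two-sided .05.

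**Assumed inputs.** Total variance 1, split into patient (s), patient-by-phase (p) and residual (e). The main setting is s = 0.5, with p from 0 to 0.2 and e = 0.5 - p. No dropout and no treatment effect.

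**True standard error.** A patient's phase mean has within-patient variance p + e/3. The difference of two phase means has variance 2(p + e/3), so averaging over 25 patients gives

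SE_true = sqrt(2(p + e/3)/25).

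**Standard error reported by the patient-intercept fit.** Six visits leave five within-patient degrees of freedom. One carries the phase difference, with expected mean square e + 3p, and four have expectation e. The pooled residual is e + 3p/5 = e + 0.6p. With 75 observations per condition,

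SE_model = sqrt(2(e + 0.6p)/75).

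**Type I error.** 2(1 - Phi(1.96 x SE_model/SE_true)).

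| s / p / e | SE_true | SE_model | ratio | type I error |
|---|---|---|---|---|
| 0.5 / 0 / 0.5 | 0.115 | 0.115 | 1.00 | 5.0% |
| 0.5 / 0.05 / 0.45 | 0.126 | 0.113 | 0.89 | 8.0% |
| 0.5 / 0.1 / 0.4 | 0.137 | 0.111 | 0.81 | 11.2% |
| 0.5 / 0.2 / 0.3 | 0.155 | 0.106 | 0.68 | 18% |

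Simulated null trials agree: about 5%, 7-8%, 11-12% and 18% in the four rows. A paired, phase-adjusted contrast (t on 23 df) stays between 4.8% and 5.3%. The two analyses disagree on significance in about 2%, 6% and 13% of null trials at p = 0, 0.1 and 0.2.

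**Small-sample method.** A REML unstructured fit by patient, with uncorrected standard error and t on 23 df, rejected in 11-14% of simulated null trials. It did so even with no patient-by-phase variance (12-13%).

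**Phase term.** Adding phase to the patient-intercept fit leaves the error at 18% in the last row, so phase alone is not the remedy. If phase is omitted and the time trend restarts in each phase, the bias is (13 - 12)/25 = 4% of any phase shift. If the trend runs over study weeks, the line absorbs 82% of a phase step, so the bias is about 0.18 x 4% = 0.7%. The loss of precision under a within-phase trend is sqrt(1 + (shift/SD)^2), where SD = sqrt(2(p + e/3)) is that of the paired difference. For shifts of 0.25 to 0.5 SD units:
- p = 0 (SD 0.577): residual SD up 9% to 32%.
- p = 0.2 (SD 0.775): residual SD up 5% to 19%.

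This makes the test conservative. The choice of trend scale moves the type I error of the patient-intercept fit by no more than 0.5 points.

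**The case against.** The strongest reply is that the text permits a valid analysis. Repeated measures in PROC MIXED points to patient as the subject, and a competent analyst could add a patient-by-phase component. The study is also called a pilot, its alpha is described as exploratory, and all the variances above are assumed. With zero patient-by-phase variance the patient-intercept fit holds 5%. All of this stands. It softens the consequence, but it does not say which test will be run, and the plan gives no reason to take that variance as zero.

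The documents do not support several stronger readings that a reader might infer.

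- That the plan commits to an invalid test. It commits to no covariance at all.
- That one wide span of error rates describes this trial. Such a span would join different covariance structures under different assumed variances.
- That the baseline covariate might be the end-of-washout score. That score will exist, since "All efficacy and safety assessments will be performed at each visit", but Screening Assessments uses baseline for the entry visit, and Data Analysis ties baseline characteristics to randomisation. The washout visit is never called a baseline.
- That counting 25 patients under each condition means they are analysed as separate people. Without dropout the count is correct, and the wording does not imply a between-patient analysis.
- That the missing phase term causes the inflation. By the figures above it does not.

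**Conclusion.** The concern holds as a gap in specification. The plan names neither a covariance that allows for correlation within a patient's phase nor a small-sample method, and it omits phase. Under an assumed patient share of 0.5 and complete data, the patient-intercept reading rejects a true null in about 5% of trials with no patient-by-phase variance, 7-8% at a share of 0.05, 11-12% at 0.1 and 18% at 0.2. These figures are conditional on the assumed shares, and the documents cannot narrow them. The covariance and its small-sample correction carry the problem. The phase term affects mainly precision. The gap should be closed before unblinding, but it does not make the trial unanalysable.

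**What to change.** State the primary model in Data Analysis:

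- fixed effects for treatment, phase (first or second), time within phase and the study-entry value of the measure;
- random effects for patient and patient-by-phase, or an equivalent covariance with patient as subject that allows correlation within a phase;
- Kenward-Roger standard errors and degrees of freedom.

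Two clarifications can go in the same edit. Say that the baseline covariate is the study-entry score. Where the section says "Demographic and baseline visit characteristics for milk thistle and placebo groups will be compared using chi-square and analysis of variance", say that the groups are the two randomised sequences, since each condition contains the same patients.

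The cost is wording and about one degree of freedom for phase, with no added data, visits or patients. Where patient-by-phase variance exists, intervals will be wider than under the patient-intercept fit: by 0.137/0.111 = 1.23 times at a share of 0.1 and 0.155/0.106 = 1.46 times at 0.2, before any change in the t quantile. That width is the correct one. If the variance is zero the test is slightly conservative: simulated fits with patient and patient-by-phase effects gave about 2.5% to 3.6%. Those runs did not establish the exact level under Kenward-Roger.

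### The crossover model has a linear time trend but no phase (period) term, so a shift common to everyone between phases can leak into the treatment effect; the effect is minor and cheap to remove

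*Combined protocol and SAP*

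**What the plan says.** The Data Analysis section sets one model for everything: "Primary and secondary measures will be examined using repeated-measures ANOVA modeling analyses". It adds two rules, "The baseline value of the measure being analyzed will be used as a covariate" and "A time trend (linear) will be included in all models", and makes the treatment main effect the test of primary interest. It names no phase, period or sequence term. It does not say whether time runs from study entry or restarts in each phase, or whether baseline means study entry or the start of each phase. All available post-randomization data are analysed first, with completers as support.

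Methodology and Study Design describe two 6-week phases separated by a 1-week wash-out, 25 people randomized 1:1 to order, and visits every two weeks within phases plus one at the end of wash-out. The method of randomization beyond 1:1 is not described.

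CGI-Improvement is a listed secondary measure under Efficacy Assessments. The scale description under Screening Assessments separates the two CGI scales: "The CGI severity scale was used at each visit", but "The CGI Improvement scale was used at each follow-up visit". The assessment list in the same section puts both scales at each visit, and Study Design says "All efficacy and safety assessments will be performed at each visit".

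**The concern.** In a two-period crossover, anything that moves everyone between the first and second phase (regression to the mean, familiarity with the ratings, season) is a phase effect. Treatment and phase are orthogonal only if the two orders are the same size. An odd total of 25 rules that out, and losses before phase 2 can widen the gap. Without a phase term, the treatment coefficient picks up part of the shift, and what the model does not absorb goes into the residual. This applies to every measure, including the primary NIMH-TSS.

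A smaller matter concerns the covariate rule. Read with the CGI scale description, the rule asks for a baseline value that CGI-Improvement does not have.

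**Working it through.** **Inputs.** N = 25 and 1:1 allocation (Methodology). On-treatment visits at weeks 2, 4, 6 and 9, 11, 13 (from Study Design). Assumptions, because the documents give none: only on-treatment ratings enter the model, participants have a random intercept (compound symmetry), and the drop-out pattern, ICC and phase-shift size are as stated below. The plan's own figure, 25 per condition, reproduces as a head count: 25 people each receive both conditions, with no losses.

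**1. How much of phase the trend absorbs.** The mean week is 7.5, with deviations ±1.5, ±3.5 and ±5.5. The sum of squares for week is 2 × (2.25 + 12.25 + 30.25) = 89.5; for phase (±0.5) it is 6 × 0.25 = 1.5; the cross-product is 2 × 0.5 × (1.5 + 3.5 + 5.5) = 10.5. So R² = 10.5² / (89.5 × 1.5) = 110.25 / 134.25 = 0.821. Week within phase takes the same values in both phases, so its R² is 0.

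**2. Leak with complete phases.** Let m be the difference in order sizes divided by N. As a share of the phase shift, in absolute value, the leak is m(1 − R²) / (1 − m²R²), which reduces to m for within-phase coding.
- 12/13: m = 1/25 = 0.040. Study week: 0.040 × 0.179 / (1 − 0.0016 × 0.821) = 0.0072. Within phase: 0.040.
- 9/13 (completer analysis if 3 of the 12 leave): m = 4/22 = 0.182. Study week 0.033; within phase 0.182.
- 10/15 (assumed): m = 0.20. Study week 0.037; within phase 0.200.

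Generalised least squares gives the same values at every ICC tried from 0 to 0.9.

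**3. Leak with all available data.** If 3 of the 12 in one order miss phase 2 but keep their phase-1 records (assumption), generalised least squares gives 0.020 to 0.035 (study week) or 0.11 to 0.18 (within phase) as ICC goes from 0 to 0.9. With a phase term the leak is 0 in every case in steps 2 and 3.

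**4. Simple randomization (assumption).** With Binomial(25, 0.5), a split of 10/15 or more uneven has probability 0.424. The mean absolute leak is 0.031 (study week) or 0.161 (within phase). Either order is equally likely to be the larger, so the signed mean is 0.

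**5. Precision at 12/13.** Take residual SD 1 and a phase shift of 1 residual SD (assumption). There are 25 × 6 = 150 records, and 150 − 27 = 123 residual degrees of freedom with participant effects, treatment and time. The treatment sum of squares is 150 × 0.25 = 37.5, so the SE with a phase term is about 1/√37.5 = 0.163.
- Within-phase trend: the shift adds about 37.5 × (1 − 0.0016) = 37.4 to the residual sum of squares. 37.4/123 = 0.304, so the SE is 0.163 × √1.304 = 0.186.
- Study-week trend: it adds about 37.5 × 0.179 = 6.7. 6.7/123 = 0.054, so the SE is 0.163 × √1.054 = about 0.168.

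A null simulation (4000 runs) gave the same standard errors. Rejection rates at nominal 5% were 3.3% (within phase), 4.6% (study week) and 4.6% (with a phase term).

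**6. CGI-Improvement.** If it is rated only at follow-up, none of the 150 records has an own-baseline value. If a baseline rating were entered as a constant (no change), intercept, treatment, time and that constant form 4 columns of rank 3: the covariate is redundant with the intercept, but treatment remains estimable. A phase-specific baseline could at best take a value from the end of wash-out for the 75 phase-2 records. With a study-entry baseline and complete data, each participant has 3 active and 3 placebo ratings, so a participant-constant covariate is orthogonal to treatment and changes the estimate by exactly 0.

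**The case against.** The best defence is that the linear trend already does most of the work. If time is coded as study week, 82% of the phase contrast is absorbed, and the leak at 12/13 is 0.007 SD for a shift of 1 SD, against a standard error near 0.17 SD in step 5. That is negligible, and the plan calls itself exploratory. This stands for study-week coding near balance. It does not cover within-phase coding, which the text equally allows, or unequal losses before phase 2. Such losses are plausible, because Study Design and Safety Assessments list several grounds for removing participants.

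Some stronger readings are tempting, but the documents do not support them.
- A reader might infer that the primary test is expected to be biased, or that false positives are inflated. Under simple randomization the signed mean leak is 0, and near balance the test is conservative. Averaged over random splits, inflation appears only if within-phase coding, simple randomization and a 1-SD shift are all assumed. The leak then has SD 5/25 = 0.20, the estimate has SD √(0.163² + 0.20²) = 0.258, and 1.96 × 0.186/0.258 = 1.41, a rejection rate near 16%. The documents state none of these three conditions.
- A reader might take 9/13 as the main analysis. It describes only the supportive completer analysis; the first analysis keeps phase-1 records.
- A reader might conclude that CGI-Improvement cannot be analysed. That it is rated only at follow-up is inferred from the contrast between the two CGI sentences, and two other places say each visit. Even with a constant baseline, the treatment effect can be estimated, and any analyst would fill the gap sensibly.

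**Conclusion.** The omission is real and applies to every measure, including the primary one, but it is minor. The leak is 0.7% or 4% of a common phase shift at 12/13 with complete data (study-week or within-phase coding). It is about 2% to 3.5%, or 11% to 18%, if 3 of 12 in one order miss phase 2 and all data are used, and 3.3% or 18% in the matching completer analysis. Near balance the main cost is a larger standard error, mostly with within-phase coding. These shares rest on the assumed random-intercept model, on-treatment visits only, and the stated drop-out or allocation scenarios. The documents give no phase-shift size, so no absolute bias can be claimed. The CGI-Improvement covariate is a clarification: with a study-entry baseline and complete data it moves no treatment estimate.

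**What to change.** Add a fixed phase (period) term to the model for all primary and secondary measures, and state whether time is coded as study week or week within phase. Weeks 9, 11 and 13 equal 7 plus weeks 2, 4 and 6, so once the phase term is in, both codings give the same treatment estimate.

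The cost is one sentence and one degree of freedom, with no new data. With complete phases, the variance of the treatment estimate rises by the factor (1 − m²R²)/(1 − m²). This is 1.0003 at 12/13 with study-week coding and 1/(1 − 0.04) = 1.042 at 10/15 with within-phase coding, so about 0.03% to 4%.

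Clarifications, one sentence each:
- Exempt CGI-Improvement from the own-baseline rule, or use baseline CGI-Severity, which is already collected. The gain is small, and nil with complete data.
- State whether baseline means study entry or start of phase.
- Reconcile Study Design, the assessment list and the CGI description on whether CGI-Improvement is rated at baseline.
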